## 4. SUBJECT DISPOSITION

### 4.1. Subject Enrollment and Disposition

A summary of subject enrollment will be provided by treatment group and overall. The summary will present the number and percentage of subjects enrolled. For each column, the denominator for the percentage calculation will be the total number of subjects analyzed for that column.

A summary of subject disposition will be provided by dose cohort. The summary will present the number of subjects in each of the following categories:

- Screened
- Enrolled
- DLT Analysis Set
- Safety Analysis Set
- Full Analysis Set
- GS-1423 completion status
  - Completed study drug dosing as specified per protocol
  - Discontinued study drug dosing with reasons
- Study completion status
  - Completed the protocol-planned duration of the study
  - Discontinued the study with reasons

For the status of study drug and study completion and reasons for discontinuation, the number and percentage of subjects in each category will be provided. The denominator for the percentage calculation will be the total number of subjects in the Safety Analysis Set corresponding to that column. In addition, a flowchart will be provided to depict the disposition.

The following by-subject listing will be provided by subject identification (ID) number in ascending order to support the above summary tables:

- Reasons for premature study drug or study discontinuation
- Reasons for screen failure (will be provided by screening ID number in ascending order)

## **4.2. Extent of Study Drug Exposure**

Extent of exposure to study drug will be examined by assessing the total duration of exposure to study drug, total number of doses, and the actual dose amount.

### **4.2.1. Exposure to GS-1423**

A listing of GS-1423 administration will be provided by subject ID number (in ascending order) and visit (in chronological order), including dosing date/time, planned dosage, actual dosage administered, infusion outcome and reason that entire dose was delayed or not administered. Exposure to GS-1423 will be summarized by cohort for the safety analysis set.

#### **4.2.1.1. Duration of Exposure**

Total duration of exposure to study drug will be defined as (last dosing date - first dosing date + 1)/7, regardless of any temporary interruptions in study drug administration, and will be expressed in weeks using up to 1 decimal place (eg, 4.5 weeks). If the last study drug dosing date is missing, the latest date among the study drug end date, clinical visit date, laboratory sample collection date, and vital signs assessment date that occurred during the on-treatment period will be used.

The total duration of exposure to study drug will be summarized using descriptive statistics. Summaries will be provided by treatment group for the Safety Analysis Set. The number and percentage of subjects who have dose interruptions, and the reasons, will be summarized by treatment.

#### **4.2.1.2. Number of Doses**

The number of doses subjects were exposed to study drug will be summarized using descriptive statistics, as well as the number and percentage of subjects exposed to the following number of doses:  $\geq 1$ ,  $\geq 2$ ,  $\geq 4$ ,  $\geq 6$ ,  $\geq 8$ ,  $\geq 10$  dose(s). A subject is said to have received a dose of GS-1423 if he/she received any amount of the planned dose of GS-1423.

#### **4.2.1.3. Actual Dose Amount**

In addition, the total and average actual dose amount received for GS-1423 in mg will be summarized using descriptive statistics (N, mean, StD, median, Q1, Q3, minimum, and maximum). The average actual dose amount of GS-1423 is defined as (total actual dose amount received in mg) / (number of doses given), regardless of whether the doses were interrupted/completed.

## **4.3. Protocol Deviations**

Subjects who did not meet the eligibility criteria for study entry, but enrolled in the study will be summarized regardless of whether they were exempted by the sponsor or not. The summary will present the number and percentage of subjects who did not meet at least 1 eligibility criterion and the number of subjects who did not meet specific criteria by treatment group based on the All

Enrolled Analysis Set. A by-subject listing will be provided for those subjects who did not meet at least 1 eligibility (inclusion or exclusion) criterion. The listing will present the eligibility criterion (or criteria if more than 1 deviation) that subjects did not meet and related comments, if collected.

Protocol deviations occurring after subjects entered the study are documented during routine monitoring. The number and percentage of subjects with important protocol deviations by deviation reason (eg, nonadherence to study drug, violation of select inclusion/exclusion criteria) will be summarized by cohorts for the All Enrolled Analysis Set. A by-subject listing will be provided for those subjects with important protocol deviation.

#### **4.4. Assessment of COVID-19 Impact**

This study was ongoing during the novel coronavirus (COVID-19) pandemic which has an impact on the study conduct. Some subjects were unable to attend onsite visits due to shelter in place guidelines, site closures, or other reasons. This section describes how special situations due to COVID-19 will be handled in the analysis.

##### **4.4.1. Study Drug or Study Discontinuation Due to COVID-19**

A by-subject listing of reasons for premature study drug or study discontinuation due to COVID-19 will be created.

##### **4.4.2. Protocol Deviations Due to COVID-19**

A by-subject listing will be provided for subjects with important protocol deviation related to COVID-19. A separate listing will be provided for subjects with non-important protocol deviation related to COVID-19.

##### **4.4.3. Missed and Virtual Visits Due to COVID-19**

A by-subject listing of subjects with missed or virtual visits due to COVID-19 will be provided by subject ID number in ascending order.

Information regarding virtual or missed visits due to COVID-19 was collected as free text in the CRF comment fields. The determination of missing or virtual visits due to COVID-19 was done using Natural Language Processing (NLP) to search the CRF comment fields. A detailed explanation of the algorithm is given in [Appendix 3](#).

##### **4.4.4. Adverse Events Due to COVID-19**

AEs of COVID-19 will be included in analyses of AEs if applicable, which will be determined through COVID-19 SMQ broad search ([Appendix 2](#)). A by-subject listing of AEs of COVID-19 will be provided if applicable.

## 5. BASELINE CHARACTERISTICS

### 5.1. Demographics and Baseline Characteristics

Subject demographic variables (ie, age, sex, race, and ethnicity) and baseline characteristics (body weight [in kg], height [in cm], body mass index [BMI; in kg/m^2], Eastern Cooperative Oncology Group (ECOG) Performance Status at baseline) will be summarized by dosage cohort and overall using descriptive statistics for continuous variables and using number and percentage of subjects for categorical variables. The ECOG status at baseline is the ECOG status at screening. The summary of demographic data will be provided for the Safety Analysis Set.

A by-subject demographic listing, including the informed consent date, will be provided by subject ID number in ascending order. A by-subject baseline characteristics will also be provided by subject ID number in ascending order.

### 5.2. Medical History

Medical history will be collected at screening for disease-specific and general conditions (ie, conditions not specific to the disease being studied).

A by-subject listing of disease-specific medical history and general medical history will be provided by subject ID number in ascending order. General medical history will not be coded.

### 5.3. Prior Anti-cancer Therapy and Radiotherapy

Number of prior regimens, time since the completion of last regimen, and time since progression in the last regimen will be summarized by treatment group using descriptive statistics based on the Safety Analysis Set.

Time since the completion of last regimen (months) will be calculated by (first dosing date of study drug – date of completion of last regimen) /30.4375. Time since progression of last regimen (months) will be calculated by (first dosing date of study drug – date of progression in last regimen)/30.4375. In deriving the time since the completion of last regimen and time since progression in the last regimen, all partial dates of last regimen will be identified, and the partial dates will be imputed as follows:

- If day and month are missing but year is available, then the imputed day and month will be 01 January.
- If day is missing but the month and year are available, then the imputed day will be the first day of the month.
- Partial date will not be imputed if the year is missing.

The details of prior anti-cancer therapy will be listed including line of therapy, type of regimen, and regimen start/stop date.

The details of prior radiotherapy and surgery will also be listed.

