### **3.7. Data Handling Conventions and Transformations**

In general, the subject's age collected at Day 1 (in years) will be used for analyses and presented in listings. If age at Day 1 is not available for a subject, then age derived based on date of birth and the Day 1 visit date will be used instead. If an enrolled subject was not dosed with any study drug, the enrollment date will be used instead of the Day 1 visit date. For screen failures, the date the first informed consent was signed will be used for the age derivation. If only the birth year is collected on the CRF, "01 July" will be used for the unknown birth day and month for the purpose of age calculation.

Non-PK data that are continuous in nature but are less than the lower limit of quantitation (LOQ) or above the upper LOQ will be imputed as follows:

- A value that is 1 unit less than the LOQ will be used to calculate descriptive statistics if the datum is reported in the form of “ $< x$ ” (where  $x$  is considered the LOQ). For example, if the values are reported as  $< 50$  and  $< 5.0$ , values of 49 and 4.9, respectively, will be used to calculate summary statistics. An exception to this rule is any value reported as  $< 1$  or  $< 0.1$ , etc. For values reported as  $< 1$  or  $< 0.1$ , a value of 0.9 or 0.09, respectively, will be used to calculate summary statistics.

- A value that is 1 unit above the LOQ will be used to calculate descriptive statistics if the datum is reported in the form of “ $> x$ ” (where x is considered the LOQ). Values with decimal points will follow the same logic as above.
- The LOQ will be used to calculate descriptive statistics if the datum is reported in the form of “ $\leq x$ ” or “ $\geq x$ ” (where x is considered the LOQ).

If methods based on the assumption that the data are normally distributed are not adequate, analyses may be performed on log-transformed data or nonparametric analysis methods may be used, as appropriate.

Sparse PK concentration values that are below the limit of quantitation (BLQ) will be presented as “BLQ” in the data listing.

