#### 7.1.5.2. Incomplete Dates

All AEs with incomplete onset dates will be imputed for TEAE determination. The imputation rules are as follows:

- If the day is missing but the month and year are available, then the imputed day will be the first day of the month or the first dosing date if they have the same month and year, whichever is later.
- If the day and month are missing but year is available, then the imputed day and month will be 01 January or the first dosing date if they have the same year, whichever is later.

An AE with completely missing onset and stop dates, or with the onset date missing and a stop date later than the first dosing date of study drug, will be considered to be treatment emergent. In addition, an AE with the onset date missing and incomplete stop date with the same or later month and year (or year alone if month is not recorded) as the first dosing date of study drug will be considered treatment emergent.

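### Two sets of partial-date rules in the SAP lack an order check: a prior regimen can be imputed to end before it began (5.3), and an adverse event that resolved before the first dose can count as treatment-emergent (7.1.5.2)

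*SAP*

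**What the plan says.** **Prior regimen (SAP 5.3).** Two descriptive variables are planned: months since completion of the last regimen and months since progression on it. Each is first dosing date minus the event date, divided by 30.4375. For incomplete dates the rule is "If day and month are missing but year is available, then the imputed day and month will be 01 January", and "If day is missing but the month and year are available, then the imputed day will be the first day of the month". Nothing is imputed if the year is missing. The same section lists "line of therapy, type of regimen, and regimen start/stop date", so a start date is part of the collected data, but the imputation rule does not refer to it.

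**Adverse-event onset (SAP 7.1.5.2).** If only the day is missing, the imputed day is "the first day of the month or the first dosing date if they have the same month and year, whichever is later". If day and month are missing, "then the imputed day and month will be 01 January or the first dosing date if they have the same year, whichever is later". Neither bullet mentions the stop date. A separate paragraph covers an onset that is wholly missing. There the stop date is used: if it is complete, the event is treatment-emergent when it stopped after the first dosing date.

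**Definitions.** Protocol 8.7.2 requires a treatment-emergent event to begin on or after the first dose. SAP 7.1.5.1 uses the same lower limit, and SAP 7.8 declares no departures from the protocol's safety analyses.

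**The concern.** An imputation rule should not contradict a date that was actually recorded, and both rules can do so.

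In 5.3, a year-only stop date for a regimen begun in that same year after 1 January is always imputed to a day before the regimen started. The derived time since completion then exceeds the time since the regimen began, which cannot happen. The same applies within a month when only the day is missing.

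In 7.1.5.2, an event with an incomplete onset and a stop date before the first dose is certainly pre-treatment, yet it receives an onset on the dosing day and enters the TEAE tables. The events exposed to this are those recorded between consent and first dose. Under Protocol 7.3 these are serious events and events related to protocol procedures, so the treatment-emergent SAE tables are exposed too. The percentage of subjects with TEAEs is a secondary endpoint of Phase 1a Part A (Protocol 8.1.3), the only part that the SAP analyses.

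**Working it through.** There is no stated figure in the plan to reproduce. The check applies the rules literally to illustrative dates, which are assumed and not taken from the documents.

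**1. Prior regimen**

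Inputs: regimen start 10 Mar 2019, stop recorded as '2019', first dose 20 Jan 2020.

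- Imputed completion under SAP 5.3: 01 Jan 2019, which is 68 days before the regimen started.
- Value under the SAP: (20 Jan 2020 − 01 Jan 2019)/30.4375 = 384/30.4375 = 12.6 months.
- Logical maximum (completion on the start day): (20 Jan 2020 − 10 Mar 2019)/30.4375 = 316/30.4375 = 10.4 months.
- Excess: 68/30.4375 = 2.2 months.

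Day-missing case: start 15 Mar 2019, stop 'Mar 2019'. Imputed completion is 01 Mar 2019, 14 days before the start.

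In general, the excess over the logical maximum is (regimen start − imputed date)/30.4375. It is at most 30/30.4375 = 0.99 month if only the day is missing, and 365/30.4375 = 12.0 months if day and month are missing.

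With completion set to the later of the imputed date and the regimen start, the main example becomes 10 Mar 2019 and 10.4 months.

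**2. Adverse-event onset**

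First dose 10 Mar 2020 in every row.

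| Recorded onset | Recorded stop | Imputed onset | Onset minus stop | TEAE under SAP | TEAE with stop-date check |
|---|---|---|---|---|---|
| 'Mar 2020' | 05 Mar 2020 | 10 Mar 2020 | +5 days | Yes | No |
| '2020' | 20 Feb 2020 | 10 Mar 2020 | +19 days | Yes | No |
| wholly missing | 05 Mar 2020 | none needed | n/a | No (stop not after first dose) | No |

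The first and third rows show the internal inconsistency. Knowing the onset month leads to the wrong class, while knowing nothing about onset leads to the right one.

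**3. How often the condition is met, given a partial onset**

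Assume that the first dose is equally likely on any day of 2020, that onset is 1 to 28 days earlier (the screening window), and that every onset–stop pair resolved before dosing has equal weight. The mean onset lead is then (2×28 + 1)/3 = 19 days.

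- Month-only onset: share falling in the dosing month = 1 − 19/30.5 = 38%.
- Year-only onset: share falling in the dosing year = 1 − 19/366 = 95%.

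These shares are conditional. The documents do not say how many pre-dose events will have partial onset dates.

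**4. Effect on a cohort percentage**

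One subject is 1/6 = 17% to 1/3 = 33% of a cohort of 3 to 6, and all of a single-subject cohort. SAP 7.1.6.1 counts each subject once per summary, so the any-TEAE row moves by this amount only if the subject has no other TEAE. Otherwise only a system organ class, preferred term or severity row can change.

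**The case against.** The best defence of 7.1.5.2 is that it leans towards calling events treatment-emergent, as the SAP does elsewhere: missing relationship counts as related (7.1.3), and wholly missing onset and stop dates count as treatment-emergent. That is a sound default when timing is ambiguous. It does not cover an event whose recorded stop date precedes the first dose, because nothing is then ambiguous.

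Data controls also reduce the problem. Protocol 7.1.2.1 asks for onset and resolution dates and times where timing relative to dosing matters. Protocol 9.1.7 provides for queries, and SAP 2.2 holds the final analysis until queries are resolved or judged unresolvable. These stand as reasons to expect few cases, but they do not change the rule for any that remain.

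For 5.3, choosing the earliest date has a real merit: it cannot place completion after the first dose when the true date came before it. A floor at the regimen start keeps that property.

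A reader might infer more than the documents support in three ways.

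- **That the SAP's partial-date rules in general ignore the other recorded date.** They do not. The wholly-missing-onset paragraph of 7.1.5.2 uses the stop date, and the concomitant-medication rules in 7.4.2 use both start and stop. The rules cited at 6.1.3 and 6.1.4 are redacted and cannot be judged.
- **That 5.3 should use a midpoint, because in SAP 3.7 the first of July "will be used for the unknown birth day and month for the purpose of age calculation".** An age calculation raises no comparable ordering problem. A midpoint here can do worse. With stop '2020' and first dose 10 Mar 2020, 01 July falls after dosing; capped at the day before, it gives 1 day. The 3-week exclusion for prior systemic therapy (Protocol 4.3) and the start of the year put the true value between 21 and 69 days, and the SAP's 69 lies inside that range. With stop 'Mar 2020' and first dose 29 Mar 2020, the 15th gives 14 days, the feasible range is 21 to 28, and the SAP gives 28.
- **That carry-over from prior therapy is misjudged.** The washout is applied as an eligibility criterion at screening, not through this variable. The visible SAP has no covariates or subgroups (3.3, 3.4) that would use it.

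**Conclusion.** The point holds in a limited form. As written, SAP 5.3 can give a completion or progression date before the regimen start, and SAP 7.1.5.2 can classify an event resolved before dosing as treatment-emergent, against Protocol 8.7.2. No visible text corrects either.

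The consequences are small. The regimen error affects descriptive baseline summaries only; in the example it gives 12.6 months against a ceiling of 10.4. The AE error needs three things together: a partial onset in the same month and year (or year) as the first dose, a stop date before that dose, and an event serious or procedure-related enough to be recorded before dosing. It should be rare.

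An effect on DLT or MTD might be inferred from the small cohorts, but nothing in the documents shows one. All example dates are illustrative, and the frequency of partial dates is unknown. The regimen check also needs a known start date, which the documents list but do not say is always complete.

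**What to change.** - **SAP 5.3:** add that the imputed completion or progression date is the later of the date given by the present rule and the regimen start date, where that date is known. Keep the earliest-date rule otherwise.
- **SAP 7.1.5.2:** add that an AE with a partial onset date whose recorded stop date is before the first dosing date is not treatment-emergent. A partial stop date should count as before only if its month and year, or year alone, are earlier than those of the first dose, in line with how 7.4.2 treats partial stop dates.

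The cost is two sentences and minor programming. No new data are needed. SAP section 1 says that the plan is finalised before database finalisation and that later changes are recorded in the study report, so either route is available.

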#### **5.4. Concomitant Cancer Related Surgeries and Procedures**

A listing of concomitant cancer related surgeries and procedures will be provided for the All Enrolled Analysis Set.

CCI

[REDACTED]

CCI

[REDACTED]

CCI

[REDACTED]

CCI

[REDACTED]

[REDACTED]

I [REDACTED]

I [REDACTED]

[REDACTED]

[figure not shown]
CCI

[REDACTED]

[REDACTED]

[REDACTED]

CCI

[REDACTED]

[REDACTED]

[REDACTED]

[REDACTED]

[REDACTED]

[REDACTED]

[REDACTED]

[REDACTED]

CCI [REDACTED]

CCI [REDACTED]

[REDACTED]

[REDACTED]

[REDACTED]

[REDACTED]

[REDACTED]

[REDACTED]

## 7. SAFETY ANALYSES

### 7.1. Adverse Events and Deaths

#### 7.1.1. Adverse Event Dictionary

Clinical and laboratory adverse events (AEs) will be coded using the current version of MedDRA. System organ class (SOC), high-level group term (HLGT), high-level term (HLT), preferred term (PT), and lower-level term (LLT) will be provided in the AE dataset.

#### 7.1.2. Adverse Event Severity

Adverse events are graded by the investigator as Grade 1, 2, 3, 4, or 5 according to CTCAE Version 5.0. The severity grade of events for which the investigator did not record will be categorized as “missing” for tabular summaries and data listings. The missing category will be listed last in summary presentation.

#### 7.1.3. Relationship of Adverse Events to Study Drug

Related AEs are those for which the investigator selected “Related” on the AE case report form (CRF) to the question of “Related to Study Treatment.” Relatedness will always default to the investigator’s choice, not that of the medical monitor. Events for which the investigator did not record relationship to study drug will be considered related to study drug for summary purposes. However, by-subject data listings will show the relationship as missing from that captured on the CRF.

#### 7.1.4. Serious Adverse Events

Serious adverse events (SAEs) will be identified and captured as SAEs if the AEs met the definitions of SAEs that were specified in the study protocol. SAEs captured and stored in the clinical database will be reconciled with the SAE database from the Gilead Global Patient Safety Department before data finalization.

#### 7.1.5. Treatment-Emergent Adverse Events

##### 7.1.5.1. Definition of Treatment-Emergent Adverse Events

Treatment-emergent adverse events (TEAEs) are defined as 1 or both of the following:

- Any AEs with an onset date on or after the study drug start date and no later than 30 days after permanent discontinuation of study drug
- Any AEs leading to premature discontinuation of study drug.

